7.2 Laboratory test evolution

For the analysis of the laboratory tests evolution, the percentage of change in each visit will be calculated with respect to the baseline view. The analysis will be performed on the safety population by treatment arm as well as by treatment arm based on age groups (<65 years; ≥ 65 years) and for the total of the population.

A listing of patients and the values of the laboratory parameters (hematology, coagulation and biochemistry) at baseline, and day 3, 7, 15 and 31 visits will be provided and those associated with an AE of any grade regardless of the relationship with plitidepsin will be highlighted.

The values of the parameters will be provided as well as the percentage change versus baseline, indicating the date and the units. Parameters will be standardized to equivalent units prior to data analysis.

Baseline value will be considered the last available value before or on the same day of the first drug administration.

7.3 Other safety evaluation

The analysis will be performed on the safety population by treatment arm as well as by treatment arm based on age groups (<65 years; ≥ 65 years). The following variables are described at baseline and on days 1, 2, 3, 4, 5, 6, 7, 15 and 31 of study treatment:

- Number and percentage of patients with alterations in the chest X-ray and the indicated anomalies will be described. The following variables will be described: no change, improvement, worsening.
- Evolution of the chest X-ray result per patient.
 - N (%) of patients with improvement in radiography on days 7, 15 and 31 after the first dose of plitidepsin
 - N (%) of patients with worsening in radiography on days 7, 15 and 31 after the first dose of plitidepsin
 - N (%) of patients with no changes in radiography on days 7, 15 and 31 after the first dose of plitidepsin
- Number and percentage of patients with ECG alterations and the detected alterations will be described.
- A list with the evolution of SaO₂ in each of the controls carried out on the patients will be provided, indicating the type of saturation (air in the room / oxygen therapy / not available).
- Change in Vital Signs (median and range) from Baseline through Day 31. Calculated using the mean value when there were more than one assessment per day will be used for blood pressure measurements. Worst value per patient, per day, will be used for the rest of measurements.
 - Blood pressure, diastolic (mm Hg)
 - Blood pressure, systolic (mm Hg)
 - Heart rate (beats per minute)
 - Respiratory rate (breaths per minute)
 - pSO₂ by pulse oximetry (%) (Room-air)

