## 10. EVALUATION CALENDAR

	Baseline	Day 1	Day 2	Day 3	Day 4	Day 5	Day 6	Day 7	Day 15 (± 1 day)	Day 31 (± 3 days) 
Informed consent 	X									
Selection criteria 	X									
Medical record	X									
Vital signs 	X	X	X	X	X	X	X	X	X	X
Demographics	X									
Physical examination	X									
Electrocardiogram 	X	X	X	X	X	X	X	X	X	X
Complete blood count 	X	X*	X	X	X	X	X	X	X	X
Biochemistry 	X	X*	X	X	X	X	X	X	X	X
Coagulation 	X	X*	X	X	X	X	X	X	X	X
C-reactive protein 	X	X*	X	X	X	X	X	X	X	X
Viral load 	X				X			X	X	X
PCR COVID-19 	X				X			X	X	X
Chest x-ray 	X	Based on clinical criteria								
Pregnancy test 	X									
Treatment		X	X	X						
Other pharmacological treatments for COVID-19 			X	X	X	X	X	X	X	X
Adverse events 	X	X	X	X	X	X	X	X	X	X

- \* It will not be necessary to repeat the tests on day 1 if they were carried out in the 24 hours prior to administration of plitidepsin.
- 1 The patient will sign the informed consent before undergoing any specific study procedure that is not part of normal clinical practice.
  - 2 The patient must meet all the inclusion criteria and none of the exclusion criteria in order to be included in the study.
  - 3 Vital signs will be measured **every 8 hours** or every nursing shift until discharge: temperature, blood pressure, heart rate, respiratory rate, O2 saturation (including oxygenation method). Once the patient has been discharged, a single measurement of vital signs will be made at the study visits detailed in the table.
  - 4 The electrocardiogram will be performed during the baseline visit and on days 1, 2, 3, 4, 5, 6, 7, 15 and 31 from the start of treatment with plitidepsin. The PR interval and the QT interval will be measured.
  - 5 Complete blood count on days 1, 2, 3, 4, 5, 6, 7, 15 and 31.
  - 6 Basic biochemistry on days 1, 2, 3, 4, 5, 6, 7, 15 and 31. It will include transaminases, bilirubin, alkaline phosphatase, LDH, CK, ferritin and troponin.
  - 7 Coagulation on days 1, 2, 3, 4, 5, 6, 7, 15 and 31, including D-dimer.
  - 8 C-reactive protein on days 1, 2, 3, 4, 5, 6, 7, 15 and 31.

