  - 9 The first time the patient tested positive for COVID-19 will be included as well. The test will be repeated in the 48 hours prior to administration of plitidepsin and on days 4, 7, 15 and 31, if negative detection does not occur before then. Qualitative PCR shall be obtained on nasopharyngeal exudate (preferably) or a sample from the lower respiratory tract.
  - 10 A chest X-ray will be performed at baseline and subsequently based on clinical discretion.
  - 11 Only fertile women.
  - 12 Patients may receive other pharmacological treatments for COVID-19 at the discretion of the investigator 24 hours after administration of the last dose of plitidepsin.
  - 13 Adverse events (serious and non-serious) will be recorded from signing of the informed consent up to 28 days after administration of the last dose of plitidepsin.
  - 14 A safety visit will be made 28 days (+3 days) after the last dose of plitidepsin.
  - 15 The viral load should be determined in a sample obtained from nasopharyngeal exudate (preferably) or a sample from the lower respiratory tract.

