3 GENERAL PRINCIPLES

Planned analyses in this document will be carried out once the database is declared cleaned, closed and approved by Pharma Mar according to the premises described in the Data Management Plan version 2.0 approved on 09 June 2020.

Statistical analyses will be performed using SAS software version 9.4 and R. The results of the analyses will be presented in editable format (i.e rtf).

The data will be provided with one decimal place in general. In those cases where greater precision is required, as many decimal places as necessary will be provided.

Before to perform the analyses, the following activities will be performed:

Codification/revision and approval of the following terms:

- Adverse events /procedures according to MedDRA dictionary (latest version available).
- Medication according to the WhoDrug dictionary (latest version available).
- Reconciliation of serious adverse events in the study between the clinical database and the Pharmacovigilance database and resolution of all discrepancies.

Analysis will be done separately for each arm and the total population.

Continuous variables will be presented through the mean, median, standard deviation, range, Q1, Q3 and categorical variables will be presented through the distribution of frequencies and percentages; missing values will not be taken into account in the percentage calculation, percentages with valid data will be presented.

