4.6 Missing data

Missing data imputation is not foreseen.

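### SAP 7.3 gives chest X-ray percentages at Days 7, 15 and 31, but films after baseline are discretionary, so the percentages do not estimate the rate in the arm

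*SAP*

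**What the plan says.** **Schedule.** In the calendar in protocol section 10, the chest X-ray row has a mark at baseline and then only "Based on clinical criteria". Footnote 10 says the same: "A chest X-ray will be performed at baseline and subsequently based on clinical discretion". No film is due on Day 7, 15 or 31.

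**Output.** SAP 7.3 lists chest X-ray first under a lead-in that reads "The following variables are described at baseline and on days 1, 2, 3, 4, 5, 6, 7, 15 and 31 of study treatment". It then asks for the number and percentage of patients improved, worsened and unchanged at three fixed days, for example "N (%) of patients with worsening in radiography on days 7, 15 and 31 after the first dose of plitidepsin". On the analysis set it says "The analysis will be performed on the safety population by treatment arm as well as by treatment arm based on age groups".

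**Denominator.** SAP section 3 sets the general rule for categorical variables: "missing values will not be taken into account in the percentage calculation, percentages with valid data will be presented". SAP 4.6 adds "Missing data imputation is not foreseen". The text of SAP 7.3 gives no X-ray denominator of its own, no count of patients imaged, no visit window and no carry-forward rule.

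**The concern.** The lead-in to SAP 7.3 fits ECG and vital signs, which the protocol calendar schedules on every day listed. It does not fit chest X-ray. At Days 7, 15 and 31 a patient has a film only if a clinician asked for one, and the valid-data rule then removes everyone else from the percentage. The table would look like a per-arm rate of radiographic change at a visit when it describes a subset chosen by clinicians.

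Two features of the design make a comparison across doses unsafe. The study is open-label, so whoever orders the film can know the dose. The arms also opened in sequence, with 1.5 mg first and 2.5 mg last, so a change in imaging practice over time would be partly mixed with dose. Neither shows that imaging did differ by arm, but nothing in the plan would let a reader tell. The planned size is 15 patients per arm, split again at age 65, so a few films can move a percentage a long way.

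**Working it through.** The plan states no figure for this output, so there is none to reproduce. The check has three parts.

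**1. The texts side by side**

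| Item | Source | Content |
|---|---|---|
| Films required | Protocol 10, calendar row and footnote 10 | Baseline only; later films discretionary |
| Films tabulated | SAP 7.3 | Days 7, 15 and 31, by arm and by age group within arm |
| Percentage rule | SAP 3 | Valid data only |
| Imputation | SAP 4.6 | None |
| Patients per arm | SAP 2.4 | 15 after the extension |

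If a film that was not taken counts as a missing value, the percentage at each day is taken over imaged patients only.

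**2. How far selection can move the percentage**

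Let p be the true share worsened in the arm, a the chance that a worsening patient is imaged, and c the chance that any other patient is imaged. The expected valid-data share is

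p·a / (p·a + (1 − p)·c).

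The documents give none of these three values. With p = 0.10 as an assumption:

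| a | c | Calculation | Reported share worsened |
|---|---|---|---|
| 0.5 | 0.8 | 0.05 / (0.05 + 0.72) = 0.05 / 0.77 | 6.5% |
| equal | equal | the imaging chance cancels | 10.0% |
| 0.8 | 0.2 | 0.08 / (0.08 + 0.18) = 0.08 / 0.26 | 30.8% |
| 1.0 | 0.1 | 0.10 / (0.10 + 0.09) = 0.10 / 0.19 | 52.6% |

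The result depends only on the ratio of c to a. The share is overstated when worsening patients are imaged more often than others, understated when they are imaged less often, and unbiased when the two chances are equal.

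**3. What the percentage hides, whoever is selected**

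Suppose 6 of the 15 patients in an arm are imaged at a given day and 2 of those have worsened (both numbers are illustrative). The valid-data figure is 2/6 = 33.3%, with an exact 95% interval of 4.3% to 77.7%. Among all 15, the share is at least 2/15 = 13.3%, if none of the 9 unimaged patients worsened. It is at most (2 + 9)/15 = 73.3%, if all of them did. This range needs no assumption about why patients were imaged, and a reader cannot work it out unless the table shows the number imaged.

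**The case against.** **The denominator is inferred.** SAP 7.3 names the safety population and does not say whether an unscheduled film is a missing value. This stands as a caution. The section 3 rule is still the only percentage rule the SAP gives that would govern this output. The other reading, all safety patients with no category for those not imaged, would silently count an unimaged patient as having no finding, and that cannot be interpreted either.

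**The table shells cannot be seen.** SAP 11.7 names chest X-ray in its title, but the text available runs from a broken-off Table 11.7.1 straight to Table 11.7.5. A shell with a count of patients imaged may exist. That is a limit on this point and not a fault in the plan. The wording of SAP 7.3 would still need to agree with such a shell.

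**The films may not be taken because a patient is getting worse.** A reader might infer that these are films taken for cause, that deteriorating patients are over-represented, and that worsening is therefore overstated two- to fivefold. The documents do not support this. Clinical criteria and discretion can also cover routine, pre-discharge or follow-up films that confirm resolution, and those could over-represent improvement. The first two rows of the second table show understatement and no bias under equally hypothetical rates.

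**The impact is limited.** This stands. Chest X-ray is neither a primary nor a secondary endpoint, the analyses are descriptive, SAP 7.3 plans no test on it, and no rule for opening a cohort or interrupting recruitment uses it. A reader might also infer that the table would be taken as a dose signal. The documents give it no such role.

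**Part of the remedy already exists.** SAP 7.3 plans the evolution of the X-ray result per patient. Tabulating films obtained in practice is legitimate if they are labelled as such, so deleting the percentages is not required.

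**Conclusion.** The point holds. The protocol schedules no film at the three days tabulated, and under the SAP's own valid-data rule each percentage would rest on patients selected by clinical discretion. It would not estimate the share improved, worsened or unchanged in the arm. This assumes that a film not taken is treated as a missing value, which is the natural reading of SAP section 3 but is not spelled out for this output.

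Selection is built into the plan, but its direction and size are unknown. With 10% truly worsening, the reported share runs from 6.5% to 52.6% over the imaging patterns shown, and it equals 10.0% if imaging does not depend on outcome. These are illustrations under assumed rates and do not estimate a bias in this trial. The output is a supporting descriptive safety item, so the matter should be corrected in the SAP but does not touch the trial's endpoints.

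**What to change.** Amend SAP 7.3 for the three chest X-ray outputs:

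- Exempt them from the valid-data rule of SAP section 3 and use all safety-population patients in the arm (or in the arm and age group) as the denominator.
- Add an explicit 'not imaged' category, and give the number imaged at each day.
- State the window within which a film counts towards Day 7, 15 or 31.
- Label the table 'films taken at clinical discretion', and state that no comparison by dose will be drawn from it.
- Support the table with the per-patient evolution already planned, adding the date of each film.

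With the 'not imaged' row, a reader can take the lowest and highest possible share directly from the table, as in the third part of the check. Any chest X-ray shell under SAP 11.7 should be brought into line.

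The cost is SAP wording and, where needed, the table shell. No extra X-rays are needed, and the decision to image stays with the clinicians. The downside is a table that looks less complete.

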## **12. STATISTICAL CONSIDERATIONS**

### **12.1. General considerations**

This section describes the main analyses that will be carried out. The statistical analysis plan to be approved by the sponsor will include additional information on analyses, management of unavailable data and analytical methods. All data will be analysed with the SAS statistical analysis system. All analyses will be carried out mainly by descriptive statistical methods. Continuous endpoints will be described using mean and standard deviation, median, minimum, maximum, Q1 and Q3. Categorical endpoints will be described with frequencies and percentages as well as the exact 95% confidence interval of the relevant study variables. All results will be presented separately by treatment arm.

The final statistical analysis that will be the basis of the final report of the study will be done on the total population of 45 patients once the extension of the study has been completed. The data of the first 27 patients will be analysed in an intermediate statistical analysis.

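### Changes in heart rate, respiratory rate and room-air saturation set worst-of-day hospital values against single post-discharge readings, and no vital-sign baseline rule is stated

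*SAP*

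**What the plan says.** Footnote 3 to the evaluation calendar (Protocol section 10) sets how often vital signs are taken. In hospital they are due every 8 hours, "or every nursing shift until discharge: temperature, blood pressure, heart rate, respiratory rate, O2 saturation (including oxygenation method"), which is about three sets a day. Afterwards the frequency drops: "Once the patient has been discharged, a single measurement of vital signs will be made at the study visits detailed in the table".

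SAP 7.3 plans to report "Change in Vital Signs (median and range) from Baseline through Day 31". It gives two rules for reducing a day's readings to one value. For systolic and diastolic pressure: "Calculated using the mean value when there were more than one assessment per day will be used for blood pressure measurements". For everything else: "Worst value per patient, per day, will be used for the rest of measurements". The parameters left under the second rule are heart rate, respiratory rate and saturation, the last listed as "pSO₂ by pulse oximetry (%) (Room-air"). The shell of Table 11.7.1 shows baseline and the change at Days 1, 2, 3, 7, 15 and 31, by dose and in total.

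SAP 7.3 does not define the vital-sign baseline. The only derivation rule for a baseline is in the laboratory section, SAP 7.2: "Baseline value will be considered the last available value before or on the same day of the first drug administration". That section concerns laboratory parameters, and its rule does not say what happens when there are several readings on the day.

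**The concern.** A daily worst value depends on how many readings were taken that day: the more readings, the more extreme the worst one. The plan takes about three readings on a hospital day and one at a post-discharge visit, then places both in the same change-from-baseline column. A difference appears even if the patient's underlying heart rate, respiratory rate and saturation are constant.

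Safety is the primary objective, and Protocol 5.2 describes the trial as uncontrolled. With no comparator that carries the same artefact, change from baseline within an arm is the natural way to read this table. An apparent recovery at Days 15 and 31, or an apparent deterioration over the dosing days, could be taken for an effect of the drug or of the disease course when part of it comes from the measurement schedule.

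**Working it through.** The plan states no figure for this point, so there is none to reproduce.

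**Inputs**
- Readings per hospital day: k about 3 (Protocol section 10, footnote 3); k = 2 and k = 4 shown as a range.
- Readings per post-discharge visit: 1 (same footnote).
- Daily value: worst of the day for heart rate, respiratory rate and room-air saturation; mean for blood pressure (SAP 7.3).
- Within-day SD and correlation between readings: not in the documents, so assumed.
- Worst is taken as the highest heart rate and respiratory rate and the lowest saturation. By symmetry the normal model gives the same size in either direction.

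**Step 1: how far the worst of k readings lies from the patient's mean for the day.** For k independent normal readings, in units of the within-patient, within-day SD,

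E[max_k] = ∫ x · k · φ(x) · Φ(x)^(k−1) dx.

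- k = 1: 0
- k = 2: 0.564
- k = 3: 3/(2√π) = 0.846
- k = 4: 1.029

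**Step 2: which visits shift.** A simulation of 400,000 patients with no true change, k = 3 and independent readings gave these median changes (the median is the statistic the SAP reports):

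| Baseline rule | Hospital days | Post-discharge visits |
|---|---|---|
| Worst of 3 | 0.00 | 0.83 SD towards improvement |
| Single reading | 0.84 SD towards worsening | 0.00 |

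With a daily-mean baseline, as for blood pressure, a single post-discharge reading gave a median change of 0.002 SD.

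**Step 3: physical units.** At k = 3 an assumed within-day heart-rate SD of 4 bpm gives 0.846 × 4 = 3.4 bpm, and 10 bpm gives 0.846 × 10 = 8.5 bpm. For respiratory rate, each 1 breath/min of within-day SD adds about 0.85 breath/min. For saturation the same multiplier is only a rough guide: saturation cannot exceed 100%, and only room-air readings count, so a patient on oxygen may have fewer than three qualifying readings in a day, or none.

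**Step 4: the unit matters.** If readings on one day have correlation ρ, the k = 3 shift in total SD (between plus within patient) is 0.846 × √(1 − ρ): 0.71 at ρ = 0.3, 0.60 at 0.5, 0.46 at 0.7, 0.38 at 0.8 and 0.27 at 0.9. The shift in bpm for a given within-day SD is unchanged; only the yardstick differs.

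**Step 5: who is on which side of discharge.** The counts under SAP Figure 15.1.2, read as patients not yet discharged, sum to 6 + 23 + 15 = 44 at day 7, 0 + 4 + 8 = 12 at day 8 and 0 + 0 + 1 = 1 at day 15. On those counts Days 1 to 7 are almost all worst-of-day values, and Days 15 and 31 almost all single readings. The SAP does not say whether these counts are final data; the mechanism does not depend on them.

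**The case against.** The strongest case on the other side has four parts.

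*Worst-of-day is a respectable safety convention.* It keeps a transient tachycardia or desaturation that a daily mean would dilute. This stands, and is a reason to keep a worst-value summary. It does not justify subtracting a worst value from a single reading.

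*The consequence is small.* Vital-sign change is not among the listed primary or secondary endpoints (Protocol 6.2 and 6.3, SAP 2.6). Protocol 12.1 says "All analyses will be carried out mainly by descriptive statistical methods", and Table 11.7.1 carries no test or decision rule. Clinically relevant abnormal vital signs are recorded separately as adverse events (Protocol 11.2.5), and Listing 11.7.6 gives each saturation value with its oxygen type. All of this stands.

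*Dose comparisons are largely spared.* A reader might infer that the artefact biases the choice of dose. The documents do not support that. All three arms follow the same schedule, and on the discharge counts nearly everyone changes from several readings to one between Day 7 and Day 15. The shift is therefore close to common across doses, except where arms differ in discharge status at a visit.

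*Not every visit is affected.* A reader might also infer that all changes from baseline are wrong. Under a worst-of-day baseline, hospital days with similar numbers of readings are compared like for like and only single-reading visits shift. Under a single-reading baseline, the post-discharge visits are unshifted and hospital days err towards worsening, the cautious direction for safety. This also stands, and makes the missing baseline rule part of the problem.

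**Conclusion.** The point holds for three parameters: heart rate, respiratory rate and room-air saturation. As written, the SAP produces a non-zero change in a patient who has not changed. The size is about 0.56, 0.85 or 1.03 within-patient, within-day SD for two, three or four hospital readings; for heart rate that is about 3.4 to 8.5 bpm at three readings if the within-day SD is 4 to 10 bpm. The direction and the visits affected depend on a baseline rule that SAP 7.3 does not give.

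Two broader readings should be avoided. It would be wrong to say that all vital signs are affected, because blood pressure uses the daily mean and has no such shift. It would also be wrong to quote 0.85 SD as an established figure: it assumes exactly three independent normal readings and is in within-day units, and the documents give neither an SD nor a correlation.

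The harm is to the within-arm time course in an uncontrolled trial. No listed endpoint, sample size or decision rule changes. One caveat: Table 11.7.1 carries footnote marks whose text is missing from the copy reviewed, so check there for a baseline rule.

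**What to change.** In SAP 7.3 and Table 11.7.1:

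- Derive change from baseline for heart rate, respiratory rate and room-air saturation from the daily mean, at baseline and at every visit. The same bullet already uses this rule for blood pressure. A single post-discharge reading is then its own mean and the expected shift is zero.
- State the vital-sign baseline rule explicitly: which day, and how several readings on that day are combined.
- Keep worst-of-day as a separate in-hospital summary for Days 1 to 7, against a baseline built the same way.

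The cost is SAP wording and one extra derivation, with no new data. The daily mean dilutes transient extremes, but the separate worst-value summary retains them. The daily mean removes the shift in location but not the difference in spread: with three independent readings a daily mean has one third of the within-day variance of a single reading. The reported ranges at post-discharge visits will therefore still tend to be wider, which a table footnote can say.
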